All subjects will be screened and recruited into the study by the research assistant coordinator. Potential subjects will meet with the research assistant coordinator who will, after an initial screening over the telephone/in person, determine eligibility based on inclusion/exclusion criteria. The initial screening will collect basic demographic information and ask questions specific to the inclusion/exclusion criteria. The initial screening will take approximately 5-10 minutes. She will explain all study procedures and risk/benefits and obtain informed consent. Subjects will undergo breath alcohol testing/urine toxicology screens at each in-person appointment to confirm self-report of drug and alcohol use information.

Admission:

Subjects will then be scheduled for admission at the CNRU for inpatient treatment, or the SAC for outpatient treatment and participation in research procedures. Subject will participate in a comprehensive physical examination conducted at the Clinical Neuroscience Research Unit (CNRU) of the CMHC to rule out any subjects who may be medically or psychiatrically unfit to participate in the study. Routine laboratory studies will include CBC, ESR, glucose, BUN/creatinine, electrolytes, liver and thyroid function tests, and EKG. Abnormal findings will be further evaluated by the physician on staff at the CNRU and appropriate medical advice will be provided. Subjects who report any specific current medical conditions and require, or are

currently on medications for treatment of their medical condition will be excluded from the study. Subjects will participate in standard substance abuse treatment.

Clinical Institute Withdrawal Assessment for Alcohol (CIWA) scores will be taken at admission to monitor alcohol withdrawal symptoms. Librium 50mg, Ativan 2mg or other treatment will be given as appropriate for clinical evidence of alcohol withdrawal symptoms. CIWA scores will be assessed every four hours for at least the first 48 hours and longer if clinically appropriate. In addition to assessing CIWA scores for PRN medication, subjects who have a history of major alcohol withdrawal symptoms (e.g. withdrawal seizures or delirium tremens) will be placed on a standing dose of Librium 50mg tid for the first 24 hours with continued treatment as clinically appropriate.

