The Structured Clinical Interview for DSM-IVTR (SCID, First et al., 1995) will be used to obtain DSM-IVTR Alcohol Dependence and other substance use disorder diagnoses. The SCID's reliability and validity among substance-using populations has been established in large-scale surveys (Kranzler et al., 1996). The number of dependence syndrome elements endorsed from the DSM-IVTR substance abuse/dependence criteria will assess severity of alcohol and other drug dependence. The SCID will also be used to obtain previous psychiatric diagnoses.

Medical History and Physical Examination: All patients will be required to participate in a physical examination including a medical history, electrocardiogram (EKG), blood and urine laboratory assessments prior to initiation of Prazosin to ensure eligibility for Prazosin study protocol. These will be conducted at the CNRU.

Short Form 36 Health Survey (SF-36) is a 36-Item questionnaire used in to assess the subjective quality of life of respondents.

Drug and Alcohol Use Measures:

Addiction Severity Index (ASI: McLellan et al., 1992) is a structured interview that assesses the severity of substance use and substance-related problems in the areas of medical, employment, legal, family/social and psychiatric functioning. The ASI is the most widely used instrument for assessment of substance use and related problems and its psychometric properties are well-established (Cacciola et al., 1997). The ASI will be used at pre-treatment and week 9. Follow-up ASI interviews will be conducted at 30 days post-treatment.

The Substance Use Calendar was developed by Miller and DelBoca (1994) and is based on the Time-Line Follow-Back Method (TLFB) (Sobell, Maisto et al. 1980). The SUC uses a calendar prompt and a number of other memory aids (e.g., holiday, payday, and other personally relevant dates) to facilitate accurate recall of daily drug use during the targeted period. It has demonstrated adequate levels of reliability and validity when administered as an in-person interview, over the telephone, and when administered via computer (e.g. Carey, 1997; Sobell, Brown, Leo, & Sobell, 1996; Sobell, Sobell, Leo & Cancilla, 1988). It's reliability and validity in drug abusing samples has also been established (Fals-Stewart, et al., 2000). In the current study we will use to obtain self-report of day to day use of alcohol and drugs, for the 60 days prior to treatment, weekly during treatment, and at the 30 day follow-up interviews.

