The MetricWire smartphone app, has been designed to be compliant with HIPAA regulations. The app encrypts data on participants' phones and while data is wirelessly transferred. The app randomly generates a 24-digit identification code that contains numbers and letters, and remains consistent for each subject throughout the smartphone assessment phase. This identification code

will be linked by the research team with the numerical Subject ID that is assigned to subjects upon their initial laboratory visit.

5. **Subject Population:** Provide a detailed description of the types of human subjects who will be recruited into this study.

One hundred and fifty treatment seeking alcohol dependent individuals (men and women) will be recruited to participate in this laboratory and medication study. Subjects will be recruited from the community without regard to sex, racial, or ethnic background. We expect a representative sample will drawn from the community.

6. **Subject classification:** Check off all classifications of subjects that will be specifically recruited for enrollment in the research project. Will subjects who may require additional safeguards or other considerations be enrolled in the study? If so, identify the population of subjects requiring special safeguards and provide a justification for their involvement.

- | | | |
|--|--|--|
|  Children |  Healthy |  Fetal material, placenta, or dead fetus |
|  Non-English Speaking |  Prisoners |  Economically disadvantaged persons |
|  Decisionally Impaired |  Employees |  Pregnant women and/or fetuses |
|  Yale Students |  Females of childbearing potential | |

NOTE: Is this research proposal designed to enroll children who are wards of the state as potential subjects? Yes No (If yes, see Instructions section VII #4 for further requirements)

7. **Inclusion/Exclusion Criteria:** What are the criteria used to determine subject inclusion or exclusion?

One hundred and fifty subjects who meet current DSM-IV criteria for alcohol dependence and are seeking treatment will be recruited to participate in this study. The following inclusion and exclusion criteria will be followed:

Inclusion Criteria:

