- i. Male or female individuals, ages 18 and above, meeting current DSM-IV criteria for alcohol dependence.
- ii. Meet current DSM-IV criteria for alcohol dependence
- iii. Subject has voluntarily given informed consent and signed the informed consent document.
- iv. Able to read English and complete study evaluations.

Exclusion Criteria:

- i. Meet current criteria for abuse or dependence on another psychoactive substance, excluding cannabis, nicotine and caffeine;

- ii. Current use of any psychoactive drugs, including anxiolytics, antidepressants (except SSRIs), naltrexone or antabuse;
- iii. Any psychotic disorder or current Axis I psychiatric symptoms requiring specific attention, including need for psychiatric medications for current major depression and anxiety disorders
- iv. Significant underlying medical conditions such as cerebral, renal, thyroid, hepatic, or cardiac pathology which in the opinion of study physician would preclude patient from fully cooperating or be of potential harm during the course of the study;
- v. Hypotensive individuals with sitting blood pressure below 90/60 mmHG.

8. How will **eligibility** be determined, and by whom?

All subjects will be screened and recruited into the study by the research assistant coordinator. Potential subjects will meet with the research assistant coordinator who will, after an initial screening over the telephone/in person, determine eligibility based on inclusion/exclusion criteria. The initial screening will collect basic demographic information and ask questions specific to the inclusion/exclusion criteria. The initial screening will take approximately 5-10 minutes. She will explain all study procedures and risk/benefits and obtain informed consent. After obtaining written informed consent for participation in the study, one of the study physicians will interview the subject and review all medical and psychiatric data prior to enrolling the subject and beginning medication.

9. **Risks:** Describe the reasonably foreseeable risks, including risks to subject privacy, discomforts, or inconveniences associated with subjects participating in the research.

i) Alcohol Detoxification:

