2. A life-threatening experience in-patient hospitalization or prolongation of existing hospitalization;
3. A persistent or significant disability or incapacity;
4. A congenital anomaly or birth defect; OR
5. Any other adverse event that, based upon appropriate medical judgment, may jeopardize the subject's health and may require medical or surgical intervention to prevent one of the other outcomes listed in this definition.

An adverse event may be graded as severe but still not meet the criteria for a Serious Adverse Event. Similarly, an adverse event may be graded as moderate but still meet the criteria for an SAE. It is important for the PI to consider the grade of the event as well as its "seriousness" when determining whether reporting to the IRB is necessary.

6. Plan for reporting UPIRSOs (including Adverse Events) to the IRB

The principal investigator will report the following types of events to the IRB:

Any incident, experience or outcome that meets ALL 3 of the following criteria:

1. Is unexpected (in terms of nature, specificity, severity, or frequency) given (a) the research procedures described in the protocol-related documents, such as the IRB-approved protocol and informed consent document and (b) the characteristics of the subject population being studied; AND
2. Is related or possibly related to participation in the research (possibly related means there is a reasonable possibility that the incident, experience, or outcome may have been caused by the procedures involved in the research); AND
3. Suggests that the research places subjects or others at greater risk of harm (including physical, psychological, economic, legal, or social harm) than was previously known or recognized.

Unanticipated Problems Involving Risks to Subjects or Others (UPIRSOs) may be medical or non-medical in nature, and include – but are not limited to – serious, unexpected, and related adverse events and unanticipated adverse device effects. Please note that adverse events are reportable to the IRB as UPIRSOs only if they meet all 3 criteria listed above.

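### Section V.7 enrols women from age 18 without addressing pregnancy or breastfeeding, and no named screening test is a pregnancy test

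*Combined protocol and SAP*

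**What the plan says.** **Eligibility.** Section V.7 admits "Male or female individuals, ages 18 and above, meeting current DSM-IV criteria for alcohol dependence". The other inclusion items repeat the diagnosis and require signed consent and the ability to read English. The exclusions cover other substance use disorders, psychoactive medication, psychiatric disorder, medical conditions and low blood pressure. The nearest to this point is exclusion iv, which begins "Significant underlying medical conditions such as cerebral, renal, thyroid, hepatic, or cardiac pathology which in the opinion of study physician would preclude patient" and goes on to conditions that could cause harm during the study. The last is "Hypotensive individuals with sitting blood pressure below 90/60 mmHG".

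**Screening tests.** Under Admission in Section V.3: "Routine laboratory studies will include CBC, ESR, glucose, BUN/creatinine, electrolytes, liver and thyroid function tests, and EKG". Under Medical History and Physical Examination, patients must have an "electrocardiogram (EKG), blood and urine laboratory assessments prior to initiation of Prazosin to ensure eligibility for Prazosin study protocol", with no list of what those blood and urine tests are. The urine screen at intake is a toxicology screen. Under Physiological Assessments, every woman gives blood at the physical for an estradiol level.

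**Subject classification.** The Section V.6 checklist has entries for "Pregnant women and/or fetuses" and "Females of childbearing potential". Neither shows a mark in the text available.

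**Exposure.** Participants take prazosin or placebo, with staff blinded (Section VI.A.3), for up to 12 weeks including the taper; some may taper earlier (Section V.3).

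**The concern.** Section V.8 has the coordinator judge eligibility by a short screen built on the Section V.7 criteria. A question that those criteria do not raise need not be asked. Pregnancy is one such question, in a trial that plans for women throughout: the dosing table in Section V.3 has separate male and female titration columns, estradiol is measured in all women, and gender is a control variable in the analysis.

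At stake is fetal or infant exposure to a blinded study drug through silence and not through a stated decision. The protocol offers nothing that would support such a decision. Its account of earlier prazosin use (Section VI.A.2) concerns hypertension, benign prostate hypertrophy, PTSD and alcohol dependence, with no data in pregnancy. The risk section (V.9) does not discuss reproductive or fetal risk.

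**Working it through.** No arithmetic bears on this point, and the plan gives no figure to reproduce. The check is a reading of every place where pregnancy or breastfeeding could be addressed before the first dose.

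| Place | What it covers | Pregnancy or breastfeeding named? |
|---|---|---|
| V.7 inclusion i–iv | Sex, age, diagnosis, consent, English | 0 of 4 |
| V.7 exclusion i–v | Substance use, drugs, psychiatric disorder, medical conditions, blood pressure | 0 of 5 |
| V.3 Admission | Itemised laboratory tests and EKG | No |
| V.3 Medical History and Physical Examination | EKG, blood and urine tests, not itemised | No |
| V.3 Urine Toxicology and Breathalyzer Screening | Toxicology at intake | No |
| V.3 Physiological Assessments | Estradiol in all women | No; compared with a later laboratory-session sample |
| V.3 Schedule of Assessments | Full assessment table | No row |

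Next, apply the text to a case. Take a woman aged 18 or over who is pregnant, meets the diagnosis, has signed consent, reads English and has a sitting pressure of at least 90/60.

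1. She meets all four inclusion criteria.
2. Exclusions i to iii and v do not apply unless she has one of those separate conditions.
3. Exclusion iv could be used against her only if the study physician treats pregnancy as a significant medical condition. Its examples are all organ disease, and it depends on the physician knowing.
4. The Admission text also excludes people who report a current medical condition and need or take medication for it. An unrecognised pregnancy, or one without medication, is not caught by that.
5. The physician reviews the medical and psychiatric data before enrolment and first dose (Section V.8). No named test puts pregnancy status among those data.

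She can therefore pass each stated step and be randomised. The same reading holds for a breastfeeding woman.

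The specimens needed for a check already exist: urine at intake, and blood from every woman at the physical. The physical comes before prazosin is started.

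**The case against.** The best case on the other side has four parts.

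- **The test list may be incomplete.** The Admission tests are introduced as inclusions and not as a closed list, and the blood and urine assessments required before prazosin are not itemised. A pregnancy test could be among them. This stands, and it limits the point to what is named.
- **The consent pages were not available.** Section VII.11 lists four consent forms, and any of them may contain pregnancy or contraception wording. This also stands. It would not repair the criteria that screening staff apply.
- **A physician decides.** Section V.8 and exclusion iv leave room to refuse a pregnant woman. That is true for a known pregnancy, but discretion without a named test is not a reliable screen for an unknown one.
- **Section V.6 proves little.** A reader might infer that V.6 and V.7 contradict each other, because the pregnancy box is blank while the criteria let pregnant women in. The documents do not support this. V.6 asks which classes the trial sets out to recruit, so a blank box is compatible with criteria that say nothing. Every box in V.6 prints blank, including the one for women of childbearing potential, and marks seem to be lost elsewhere: in Section III the grant box is blank beside the grant number. Other checklists, such as those in Sections II.1 and VII.2, do keep their marks, so loss is possible but not certain. V.6 is context only.

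A reader might also take "A congenital anomaly or birth defect" in the serious adverse event list as a sign that the trial expects such outcomes. It reads as a standard definition, in a monitoring plan that the form tells investigators to adapt from a template, and it carries no weight here.

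**Conclusion.** The gap is real and worth correcting. Women are enrolled, no criterion deals with pregnancy or breastfeeding, and no named test would detect pregnancy before up to 12 weeks of blinded treatment. The criteria do not invite pregnant women; they fail to screen them out.

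The size cannot be put as a count of people at risk. The target is 150, with 75 per arm in the dosing table, but the sex split is not given, there is no upper age limit, and half of any affected women would be on placebo. A head count built on an assumed share of women would mostly count women who are not pregnant. What can be said is that the gap covers every woman of childbearing potential who is screened.

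The conclusion assumes that the un-itemised blood and urine tests and the unavailable consent pages contain no pregnancy check. If they do, what remains is to name that check in the protocol and align the criteria with it.

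**What to change.** Reconcile Section V.6, Section V.7 and the named screening tests so that all three give the same answer on whether pregnant and breastfeeding women are eligible. Which answer is for the sponsor and investigators to decide.

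- If they are not eligible, state this in Section V.7, name a pregnancy test among the screening tests, and verify pregnancy status before the first dose on the intake urine or the blood already drawn from women at the physical. V.6 has no entry for breastfeeding, so that part must be stated in V.7.
- If they are eligible, declare pregnant women in V.6 with the justification and safeguards the form asks for, and address breastfeeding in V.7.

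In either case, confirm that the V.6 marks are as intended, itemise the blood and urine tests required before prazosin, and check that the consent forms agree.

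The cost is a short amendment and, on the first route, an inexpensive assay on a specimen already collected and a few more screen failures. The randomisation and the analysis do not change.

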Subjects who are deemed eligible, but are unable to commit to 3 - 4 weeks of inpatient treatment will be seen 2 times per week in outpatient treatment at the Yale Stress Center at [name]. Outpatient appointments will include motivational enhancement, urine drug screens, breathalyzers, blood pressure monitoring, and counseling. Daily interactive voice response (IVR) telephone monitoring, or the smartphone app MetricWire, will prompt subjects to take study medication, and assess their alcohol use, craving, craving resistance and mood states. Blood draws will be done at weeks 4-5 to measure Prazosin levels. These levels will allow staff to ensure subjects are taking medication as prescribed. Medication compliance will also be monitored through the use of riboflavin as a marker. Riboflavin produces a bright yellow discoloration of the urine when the medication is taken 2 to 8 hours prior. After the first week all subjects will be taking morning and bedtimes doses of the medication. After this time, staff will easily be able to visually inspect the subject's urine to determine whether the morning dose has been taken. 25mg of riboflavin will be added to all doses of Prazosin and placebo by the pharmacist when capsules are made. Thirty-two cc's of whole blood will be also collected from patients at intake for the purposes of understanding genetic factors that may affect craving.

In the event that someone is unable to achieve any period of abstinence within a 4-week period, they will be offered inpatient treatment or referred to a higher level of care at another facility. In the event that someone achieves abstinence but has occasional relapses, outpatient treatment will continue until they either sustain abstinence or a higher level of care is clinically indicated. These clinical judgments will be made by the principle investigator. Subjects will be provided with dollar amounts for kept appointments. Rewarding subjects for kept appointments, regardless of whether their urine is clean or not, will enable us to maintain treatment compliance while allowing for test of efficacy of medication in this trial.

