After a subject is able to abstain from substances for a period of 21+ days, they will have the option to complete a 3-night stay on the CNRU, where they will participate in imagery training and 3 laboratory sessions. After completion of the laboratory sessions, subjects will be discharged from the inpatient unit at least one day after the laboratory sessions.

Subjects will undergo the same titration onto study medication as outlined above. If the subject decides to complete the laboratory component, they will be maintained on 16.0mg dose of PRZ/PLA medication during the week of the inpatient laboratory sessions, after which they will undergo the above mentioned taper or continue to take their medication for 9 weeks in outpatient

treatment. In the event that someone continues to use alcohol while in the study, they may be asked to come in for more frequent appointments to assess for adverse symptomatology and meet with the study psychiatrist. Similar methods have been used in our outpatient lofexidine study and no adverse interaction events are anticipated.

Table 1: PRZ/PLA Dosing

	Prazosin PRZ (N = 75) (Male / Female)			Placebo (PLA) (N = 75) (Male / Female)		
Week 1	AM	PM	Evening	AM	PM	Evening
Days 1 -2 (1mg / 1mg)	0mg / 0mg	0mg / 0mg	1mg / 1mg	0mg / 0mg	0mg / 0mg	1mg / 1mg
Days 3 (2mg /1mg)	1mg / 0mg	0mg / 0mg	1mg / 1mg	1mg / 0mg	0mg / 0mg	1mg / 1mg
Days 4-6 (6 mg/4mg)	2mg/1mg	2mg/1 mg	2 mg/2mg	2mg/1mg	2mg/1 mg	2mg/2mg
Week 2						
Days 7-9 (10mg /8mg)	3mg / 2mg	3mg / 2mg	4mg /4mg	3mg / 2mg	3mg / 2mg	4mg /4mg
Days 10 – 13 (12mg/12mg)	4mg /4mg	4mg/4mg	4mg /4mg	4mg /4mg	4mg /4mg	4mg /4mg
Day 14 (16mg/16mg)	5mg/5mg	5mg/5mg	6mg/6mg	5mg/5mg	5mg/5mg	6mg/6mg

Follow-up:

Upon completion of outpatient treatment, follow-up interviews will be scheduled with all subjects. If a subject decides to complete only the inpatient phase, follow-up appointments will be scheduled after the inpatient phase is complete. Follow up interviews will be scheduled at 30 days. Urine monitoring, assessment of craving, cocaine abstinence symptoms, self report of drug use and stress and craving scales, will be assessed during the follow-up appointment.

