All subjects will also be seen two times per week in outpatient treatment at the Yale Stress Center. All subjects will participate in 1x per week standard individual drug counseling as outlined in the Individual Drug Counseling Manual (IDC, Mercer & Woody, 1998) during the outpatient trial. Each subject will be assigned a counselor with expertise in IDC. The general purpose of the counseling sessions as described in the manual are to: (1) acquire information about important concepts and aspects of recovery from addiction; (2) increase self-awareness of specific problems and issues in relation to addiction and recovery, and (3) learn new coping skills to deal with problems contributing to or resulting from the addiction and to improve functioning. The focus of this psycho-educational approach is on providing patients with frequent supportive contact, introduce them to key concepts about the recovery approach, and develop a sense of personal responsibility for recovery.

Relapse in the pilot study will be defined as the first day of any alcohol use as documented by self-report and/or positive urine and positive breathalyzer for alcohol. Treatment drop-out is defined as four consecutive missed research appointments for medication self-administration. Relapse to alcohol will be recorded in the data and subjects will continue in the protocol. Furthermore, it will be addressed by their counselor and doctor in therapy appointments. If subjects have missed four consecutive appointments, all attempts will be made to bring the subject back and after a full assessment of the subject's need, a formal referral will be made to appropriate residential, inpatient or intensive outpatient care. Subjects will be maintained in regular treatment until they have entered treatment at the next appropriate level of care. Other clinical deterioration such as exacerbation of psychiatric or withdrawal symptoms will be assessed on a case-by-case basis by the study investigators. When clinically indicated and necessary, psychotropic medication or discontinuation of study medication will be initiated and/or a referral will be made to intensive outpatient, residential or inpatient care.

Physiological Assessments

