The risks associated with stopping drinking may include: anxiety, shakiness, confusion, rapid heart rate, fever and in rare cases, life-threatening seizures. To achieve abstinence from alcohol dependence, participants are reinforced for abstinence using the fishbowl and monitored three times weekly. The Clinical Institute Withdrawal Assessment – Alcohol Revised (CIWA-Ar) will be used during this period to assess withdrawal symptoms. In the case of moderate symptoms of alcohol withdrawal (CIWA score between 8-12), study physician, [name] will provide initial treatment and monitoring and we will facilitate referral for detoxification at Southern Connecticut Rehabilitation Center (SCRC), with whom the study PI and the Stress Center research staff have a good working relationship for such transfers. Please note that the SCRC facility is only 2 blocks away from the Yale Stress Center. In cases of severe alcohol withdrawal (CIWA-Ar scores at 13 or above), the subject will be immediately transported to the Yale New Haven Hospital Emergency Room (Yale ER) for full medical assessment and treatment of alcohol withdrawal. After the subject completes detoxification he/she will be allowed to return to the study for enrollment and participation. We will continue to monitor for alcohol withdrawal throughout the study period and facilitate referral to higher level of care such as inpatient treatment, as needed. If the subject is unable to stay abstinent from alcohol, he will be withdrawn from the study and also referred to inpatient and intensive outpatient treatment for alcohol use disorders.

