Prazosin (marketed by Pfizer) is an alpha-1-adrenergic agonist, that is known to preferentially bind to post-synaptic alpha1-adrenergic receptors that are highly concentrated in the prefrontal cortical regions (Taylor & Raskind, 2002). It has been shown to have beneficial effects on PTSD symptoms (Taylor et al., 2006; Taylor & Raskind, 2000) and recent data has supported it's use in alcohol/cocaine dependence (Simpson et al., in press; Zhang & Kosten, 2005). The major advantage that Prazosin has over clonidine is that it is less sedating and with less hypotensive effects than clonidine. More specifically, Clonidine is a non-selective agonist of alpha 2a, 2 b and 2c receptors, which accounts for its sedative and hypotensive effects. Conversely, Prazosin and guanfacine are preferential for the alpha-1 and alpha-2a receptors respectively; thus, limiting sedative and hypotensive effects (Arnsten et al., 1988). Additionally, the plasma half life of Prazosin is 2-3 hours, compared to 4-10 hours for clonidine (Physician Desk Reference, 2007), allowing rapid titration and limiting accumulation of the drug.

Studies using Prazosin in patients with PTSD and alcohol dependence have used doses ranging from 2 to 16 mg/day. Commonly reported side effects with Prazosin have been fatigue, sedation and light-headedness, which are generally rated as mild in intensity. Possible side effects commonly associated with Prazosin include: low blood pressure, some drowsiness, dryness of mouth and/or throat and dizziness. No serious side effects have been noted in adult populations. There is no evidence that Prazosin will pose a greater risk to the pilot study population. Subjects will not be started on the study medication until no alcohol is present in their system. Throughout the study, subjects will be monitored for alcohol consumption. If a subject were to resume using alcohol, study medication will be discontinued.

iii) Laboratory Sessions:

(a) Intravenous (IV) Catheter: When an IV is started, there is some risk that subjects may develop a bruise or bleeding where the vein is punctured. If this occurs, appropriate treatment will be instituted immediately. On extremely rare occasions, fainting, blood clot or infection may occur.

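### The protocol gives different rules for study drug when a participant drinks, and drinking is the primary outcome

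*Combined protocol and SAP*

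**What the plan says.** The Combined protocol and SAP describes the response to drinking in four places.

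- **Section V, item 9 Risks, ii) Prazosin Treatment.** "If a subject were to resume using alcohol, study medication will be discontinued". This is unconditional.
- **Section V, item 3 Research Plan, Outpatient Plan.** "In the event that someone achieves abstinence but has occasional relapses, outpatient treatment will continue", until abstinence is sustained or higher care is indicated, as judged by the principal investigator. For those who never become abstinent: "In the event that someone is unable to achieve any period of abstinence within a 4-week period, they will be offered inpatient treatment", or else referred. For those who keep drinking: "In the event that someone continues to use alcohol while in the study, they may be asked to come in for more frequent appointments", with a check for adverse symptoms and a meeting with the study psychiatrist. The plan then adds: "Similar methods have been used in our outpatient lofexidine study and no adverse interaction events are anticipated".
- **Section V, item 3, General Procedures (end of the Admission text).** Relapse is the first day of any alcohol use. "Relapse to alcohol will be recorded in the data and subjects will continue in the protocol". Other deterioration, psychiatric or withdrawal-related, is assessed case by case: "When clinically indicated and necessary, psychotropic medication or discontinuation of study medication will be initiated", with or without referral.
- **Section V, item 9 Risks, i) Alcohol Detoxification.** The paragraph closes: "If the subject is unable to stay abstinent from alcohol, he will be withdrawn from the study", with referral elsewhere.

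Section V, item 12 makes heavy drinking days and any drinking days over 12 weeks the primary outcomes, analysed by intent to treat. A three-level dropout/withdrawn variable is a control variable in every model.

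**The concern.** The event that triggers these rules is the event the trial counts. If study drug stops at the first drink, exposure depends on the outcome. If drinkers stay on drug, it does not. If a participant who cannot stay abstinent leaves the study, observation depends on the outcome as well.

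Each policy could be defended if it were stated. Without one stated rule, two staff members could handle the same lapse differently and each cite the protocol, and the result could not be tied to a defined treatment policy. There is also a safety side. Section VI, A.2 notes that alcohol is not advised with prazosin, so staff need a single instruction.

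**Working it through.** The plan states no figure on this point, so the check is a comparison of texts plus one count of days.

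**Comparison of the texts**

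| Text | Study drug after a drink | Participation after a drink |
|---|---|---|
| Risks, Prazosin Treatment | Stops; no threshold or restart rule | Not stated |
| Outpatient Plan | Implied to continue | Continues; referral possible |
| General Procedures | Not stated for relapse | Continues |
| Risks, Alcohol Detoxification | Not stated | Ends, if the sentence applies on trial |

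1. *Prazosin Treatment against General Procedures.* These can be reconciled: drug off, participant still followed. General Procedures names stopping study medication only as a case-by-case step for other deterioration, so it does not itself make relapse a stop. It does not forbid one either.
2. *Prazosin Treatment against the Outpatient Plan.* These do not fit well. An assurance about interactions in people who keep drinking makes sense only if drug and alcohol overlap. The same plan pays for kept visits whatever the urine result, and gives as a reason that this lets the medication's efficacy be tested. Section VI, A.3 points the same way: one daily call or app prompts dosing and asks about drinking.
3. *Detoxification against General Procedures.* The surrounding sentences send people for detoxification and let them return to enrol, which suggests an entry rule. But the withdrawal sentence comes directly after one on monitoring for the whole study. Read as an on-trial rule, it contradicts General Procedures and would cut off the outcome record.

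**What differs for the analysis.** The Prazosin Treatment text gives a plasma half-life of 2–3 hours, so little drug would carry over after a stop. With stop-at-first-drink and no restart, nearly every later drinking day falls off drug, and prazosin acts mainly by preventing or delaying the first drink. If drug continues, it can also reduce drinking after a lapse. Intent to treat estimates whichever policy was applied.

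**Count of days.** Assume drug stops on the day k of the first drink and is not restarted. The window is 12 × 7 = 84 days, and the share after the stop is (84 − k)/84. The days k are illustrative.

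- k = 7: 77/84 = 91.7%
- k = 14: 70/84 = 83.3%
- k = 28: 56/84 = 66.7%
- k = 56: 28/84 = 33.3%

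The planned week-12 taper falls within these days. The figures show how far exposure could differ between the two policies for one participant. They do not measure bias or loss of power.

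**The case against.** The strongest reply is that the texts govern different things. One rule is about medication and the other about participation, and stopping drug while continuing follow-up is a coherent intent-to-treat policy. Outpatient treatment includes counselling, so its continuing need not mean that drug continues. A psychiatrist review fits a decision about drug. The principal investigator makes the Outpatient Plan judgments at a single centre, which limits inconsistency.

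Much of this stands. It disposes of any claim that Prazosin Treatment and General Procedures flatly contradict each other. It does not explain the interaction assurance or the stated aim of testing medication efficacy in people who may be drinking, and no text says which rule prevails.

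A reader might infer three stronger points that the documents do not support:

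- *That drinkers are dropped and their outcomes lost.* This needs the on-trial reading of the detoxification sentence, which is the less likely one. For relapsers who stay in, General Procedures, the weekly Substance Use Calendar, the retention procedures and the 30-day interview cover most of the record. What is missing is an explicit sentence that collection runs to week 12 after a drug stop or withdrawal.
- *That the model is wrong because an early drinker never reaches full dose yet counts in weeks 3–12.* That is ordinary intent to treat. The phase already includes people held at a lower tolerated dose.
- *That a drug stop is already coded as dropout.* Drop-out is defined by four consecutive missed appointments. The control variable also covers withdrawn participants, a term the analysis section does not define, so a clarifying line is enough.

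**Conclusion.** The inconsistency is real and should be fixed, but it is not a defect that invalidates the trial. The firm part is the conflict between the unconditional drug stop and the Outpatient Plan. The detoxification sentence adds a second, conditional problem. Stopping drug on drinking is a legitimate safety choice, and intent to treat under one stated rule with complete drinking data is a valid target.

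A reader might want to turn this into a power loss, or apply the pilot abstinence proportions to predict unequal stopping by arm. The documents do not support either. They do not say how often the stop would be applied, when, or how much effect would be lost, and the pilot arms had 7 and 10 people. The effect on bias or power therefore cannot be determined. The day shares rest on the assumed immediate stop without restart and on illustrative days.

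**What to change.** 1. Put one rule in the Outpatient Plan, General Procedures and Prazosin Treatment texts: whether drinking stops study drug, at what threshold, and whether drug may restart. The investigator makes this choice on safety grounds.
2. Limit the withdrawal sentence under Alcohol Detoxification to the pre-enrolment detoxification phase, or to study medication.
3. State that stopping drug because of drinking does not end participation. Daily telephone or app reports and the Substance Use Calendar continue to week 12 for every randomised participant who still consents, and these data enter the intent-to-treat analysis. A drug stop alone is not coded as dropout or withdrawn in the item 12 control variable.

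The reporting tools, calendar and retention procedures already exist. The cost is a wording amendment and some extra contact effort for participants who are off drug.
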